13.2.2 Decisional process for escalation to next administration duration

Following the completion of each cohort, the Sponsor Medical Expert will be provided with a summary of the observed tolerability, detailing each TEAE reported up to 60 min after the end of infusion of T and up to subject's discharge on Day 2. The Investigator will provide his assessments on severity and relationship to T. The Investigator will also provide a conclusion on the systemic and local tolerability related to the administration duration of T tested in the cohort, including his suggestion whether to consider safe to proceed with treating the next cohort of subjects with the next predefined infusion duration of T.

If the safety data obtained from a T treated cohort are considered as not sufficient for taking a decision on the infusion duration de-escalation process, and if additional safety data are deemed necessary to allow such decision to be taken, the study Investigator and the Sponsor Medical Expert may decide to add additional subjects (up to a maximum of 4 subjects per cohort) to the 10 subjects of the treated cohort.

The Sponsor Medical Expert will confirm the Sponsor's agreement to proceed or not with the treatment of the next planned subjects' cohort / injection duration.

Study Part A will be stopped if any of the following criteria is met:

1. Any serious adverse event (SAE) assessed as at least possibly related to T experienced within 60 min after the end of T injection by at least one subject in a cohort.
2. Any AE coded with the same preferred term (PT) occurring to 2 subjects of the same cohort with both AEs judged at least as possibly related to T and of severe intensity, within 60 min after the end of T injection.
3. Any AE coded with the same PT occurring to 3 (or more) subjects of the same cohort with the AEs judged at least as possibly related to T and of moderate intensity, within 60 min after the end of T injection.

At the end of study Part A, the Sponsor will take a final decision whether to proceed with study Part B with the resulting shortest injection duration considered as adequate in terms of safety determined in study Part A.

The shortest injection duration selected based on the safety and tolerability results of **Part A**, will be applied in **Part B**.

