13.2 Decisional process for escalation to next administration duration

All TEAEs will be recorded in the CRF. TEAEs will be assessed by the Investigator with focus on general safety and local tolerability (i.e., any TEAEs appearing after start of injection and interesting the injection arm).

Following all planned subject's safety assessments and before subject's discharge, the Investigator will evaluate the reported TEAEs.

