13.2.1 Decisional process for treatment of subjects within the cohorts

Subjects belonging to cohort 2, 3 and 4 will be sequentially treated as 3 subgroups of 3, 3 and 4 subjects respectively, in each cohort.

Following the treatment of the first 3 subjects in the cohort, the collected safety parameters will be carefully assessed by the Investigator. In particular, the local tolerability will be evaluated in view of confirming the treatment of the next subgroup of 3 subjects in the same cohort. If deemed necessary, the study Investigator will contact the Sponsor Medical Expert and seek advice.

The same process will be repeated following the second subgroup of 3 subjects for confirming the treatment of the last 4 subjects of the cohort.

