All the scheduled samples will be collected at the given times counted from the start of the injection/infusion. However, if, for whatever reason, a premature interruption of injection/infusion is needed or if a duration longer than that initially scheduled is needed, the sampling scheduled at the end of injection/infusion is to be moved to the actual end time. Actual sampling times for each subject will be recorded in the individual CRFs. The actual sampling times should not exceed the recommended tolerance ranges presented in the following table. Any deviation outside the recommended ranges will be verified through Data Clarification Forms and, if confirmed, will be reported as protocol deviation, although it will not automatically lead to the exclusion of the concerned subjects from the PK Sets.

Table 14.5.1.2 Tolerance ranges for the scheduled blood sampling times for PK analysis

Sampling time	Tolerance range
Pre-dose (0)	Within 30 min before T or R treatment administration
2 min, 5 min, 10 min, 15 min, 20 min, 30 min	0 min
45 min, 1 h, 1.5 h, 2 h	± 2 min
3 h, 4 h, 8 h, 12 h, 24 h	± 5 min
48 h, 72 h, 96 h, 120 h, 144 h, 168 h, 192 h, 216 h, 240 h	± 60 min

Actual sampling times for each volunteer will be recorded in the individual CRFs.

Blood samples (6 mL each) for PK analysis will be collected using an indwelling catheter with switch valve during confinement. The indwelling catheter for blood collection will be placed on the contralateral arm with respect to the infusion arm. The cannula will be rinsed, after each sampling, with about 1 mL of sterile saline solution containing 20 I.U./mL Na-heparin. The first 1.5 mL of blood will be discarded at each collection time to wash the cannula out of saline

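### The three Part A stopping criteria count from the end of the T injection, so read literally a related reaction confined to the injection cannot trigger a mandatory stop

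*Protocol*

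**What the plan says.** Section 13.2.2 of the Protocol lists the criteria under which Part A must stop.

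- Criterion 1: "Any serious adverse event (SAE) assessed as at least possibly related to T experienced within 60 min after the end of T injection", in at least one subject of a cohort.
- Criterion 2: the same preferred term in 2 subjects of a cohort, "with both AEs judged at least as possibly related to T and of severe intensity, within 60 min after the end of T injection".
- Criterion 3: the same preferred term in 3 or more subjects of a cohort, related and "of moderate intensity, within 60 min after the end of T injection".

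Nearby text sets the time differently. The cohort summary sent to the Sponsor Medical Expert, also in section 13.2.2, is described as "detailing each TEAE reported up to 60 min after the end of infusion of T" and continues to discharge on Day 2. Section 13.2 describes local tolerability events as "any TEAEs appearing after start of injection and interesting the injection arm". Both include the injection itself.

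Within cohorts 2 to 4, section 13.2.1 adds a review after each of the first two subgroups. After the first, "the local tolerability will be evaluated in view of confirming the treatment of the next subgroup of 3 subjects" in the same cohort. This review has no numeric trigger.

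**The concern.** The issue is where the window opens, not its 60-min length. Part A shortens the injection from 30 to 2 min to find the shortest tolerable duration, and the injection is when the tested rate is applied. A rate-related reaction, such as pain in the injection arm, could begin then. If the criteria are applied as worded, such a reaction does not count towards the mandatory stop when it is over before the injection ends. If it carries on past the end, whether it counts under criteria 2 and 3 depends on whether an event is placed by its onset or by its presence, which the protocol does not say.

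At stake is a predefined safety rule that could stay silent on a cluster of related moderate or severe reactions, leaving the decision to judgement alone.

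**Working it through.** There is no stated figure to reproduce: section 17.2 says the Part A cohort sizes have no statistical basis. The check is mainly a comparison of wording.

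**1. The windows side by side**

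| Place in the Protocol | Opens | Closes |
|---|---|---|
| 13.2.2, criteria 1, 2 and 3 | end of T injection | 60 min later |
| 13.2.2, cohort summary | open (includes the injection) | 60 min after the end, and on to discharge on Day 2 |
| 13.2, local tolerability | start of injection | not stated |

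None of the three criteria mentions the start of injection, the time during it, or onset. No other section extends their window backwards.

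**2. How events fall under the criteria, read literally**

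- Starts and resolves during the injection: outside all three.
- Starts during the injection and persists: criterion 1 speaks of an event being experienced in the window, so presence may suffice. Criteria 2 and 3 speak of events occurring to subjects, which can mean onset. The status is unclear.
- Starts in the 60 min after the end: inside.

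The second group is foreseeable. Section 18.3.1 allows that a severe event may lead to treatment being stopped. Each Part A subject receives one injection, so treatment can be stopped only while it is running, and a severe event that stops it must have begun before its end. Section 14.5.1 also provides for premature interruption, in which case "the sampling scheduled at the end of injection/infusion is to be moved to the actual end time". That is a blood-sampling rule. It shows only that interruption is expected and that the end is then taken as the actual end.

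**3. Clock time not covered**

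For an injection of d minutes, the uncovered time is d, and its share of the period from start to 60 min after the end is d/(d + 60).

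| Cohort | d (min) | d + 60 (min) | Share not covered |
|---|---|---|---|
| 1 | 30 | 90 | 33.3% |
| 2 | 15 | 75 | 20.0% |
| 3 | 5 | 65 | 7.7% |
| 4 | 2 | 62 | 3.2% |

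The gap is shortest at the fastest rates. Clock time is not a measure of risk, because reactions need not be spread evenly over the period.

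**4. Effect at the thresholds**

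Take a cohort that just meets a criterion, with one of the events confined to the injection:

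- Criterion 1: 1 − 1 = 0 counted, 1 needed.
- Criterion 2: 2 − 1 = 1 counted, 2 needed.
- Criterion 3: 3 − 1 = 2 counted, 3 needed.

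The mandatory stop is lost each time.

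**5. Illustration under assumed rates**

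Let p be the true probability per subject of a related moderate event with a given preferred term, and f the fraction of such events confined to the injection. Neither value is in the protocol. The number counted among 10 subjects is binomial with probability p(1 − f), and criterion 3 needs at least 3.

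| p | f = 0 | f = 0.25 | f = 0.50 |
|---|---|---|---|
| 0.20 | 0.322 | 0.180 | 0.070 |
| 0.30 | 0.617 | 0.398 | 0.180 |
| 0.50 | 0.945 | 0.789 | 0.474 |

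If every event is confined to the injection, the probability is 0 at any p. The table shows how sensitive the rule is to f. It does not estimate f.

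**The case against.** The strongest reply is that the 60 min is meant as an outer limit. The cohort summary in the same section and the local-event definition in section 13.2 both include the injection, and section 14 explains that safety timings are given from the end of infusion throughout. This is good evidence of intent, and the authors probably meant to include the injection. It does not change what the criteria say, and it is a reason to align them.

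Second, the clearly excluded set is small. An SAE as defined in section 18.2 is unlikely to begin and fully end within 2 or 5 min. An event that halts the injection is present at its end. The common drug-related events listed in section 8.4, such as headache, constipation and infusion site thrombosis, are not typically that brief. This has force, most of all for criterion 1. It has less for criteria 2 and 3, where a short reaction of moderate or severe intensity during a fast injection is conceivable and where persisting events remain unclear.

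Third, there are other safeguards. Section 10.1.2 makes each shorter duration conditional on the previous one proving safe and well tolerated, and has results reviewed after cohort 1 and after every later subgroup. The primary endpoint in section 16.1.1.1 covers events to 24 h, and section 19.2 lets the investigator or the sponsor stop the study at any time. All of this stands and limits the consequence. These steps rest on judgement, however, whereas the three criteria are there to make a stop independent of it.

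**Conclusion.** The concern holds as a wording gap in a mandatory safety rule. Read literally, all three criteria leave out related reactions confined to the T injection, and criteria 2 and 3 do not settle the status of those that begin during it and persist.

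The uncovered time is 30, 15, 5 and 2 min in cohorts 1 to 4, and one uncounted event at the threshold is enough to lose a mandatory stop. The effect on the probability of stopping cannot be determined from the protocol. The conclusion rests on the literal reading and needs no assumed event rate. The likely intent and the discretionary reviews reduce the practical risk, so this is a correction that should be made rather than a flaw that undermines Part A. No estimate or power figure is affected.

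**What to change.** In criteria 1, 2 and 3 of section 13.2.2, replace the present window with: *from the start of T injection until 60 min after its end, whether the injection was completed or interrupted*. State that events with onset during the injection count, including any that cause an interruption.

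The window would then last 90, 75, 65 and 62 min in cohorts 1 to 4, in place of 60 min in each, and would agree with section 13.2 and the cohort summary on when it opens. The cost is a few words in three criteria, with no added procedure.

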13.3 Diet and lifestyle

During the subjects' confinement at the Phase I Unit, they will not take any food or drinks (except water) for about 10 h (i.e., overnight) before P, T or R. Water will be allowed as desired, except for 1 h before and 1 h after P, T or R administration start. In order to maintain an adequate hydration, the subjects will be encouraged to drink at least 180 mL of still mineral water every 2 h for 5 h post-dose, starting at 1 h post-dose.

On Day 1 of Part A and B and on Day 3 of period 1 (Part B), the subjects will remain fasted until 5 h after the start of injection/infusion. Standardized lunch and dinner will be served at approximately 5 h and 12 h after the start of injection/infusion.

On Day -1 of each study part and period, a standardized low-fat dinner will be served.

One cup of coffee or tea will be allowed after each meal only; any other coffee, tea or food containing xanthines (i.e., coke, energy drinks, chocolate, etc.), alcohol and grapefruit will be forbidden during confinement. In particular, grapefruit and any other food or beverage known to interfere with cytochrome P450 will be forbidden for 7 days (168 h) before the first study treatment administration until the end of the study.

During confinements, smoking will be forbidden.

During confinement, routine ambulant daily activities will be strongly recommended.

13.3.1 *Restrictions*

In Part A, the subjects will be confined from the evening preceding T or R α (undiluted R) treatment (study Day -1) until the morning of Day 2. In Part B, the subjects will be confined from the evening preceding P treatment (study Day -1) until the morning of Day 5 in period 1 and from the evening preceding T or R treatment (study Day -1) until the morning of Day 3 in period 2. All other study visits will be ambulatory.

During confinement, hazardous, strenuous or athletic activities will not be permitted.

14 DESCRIPTION OF SPECIFIC PROCEDURES

NB: the PK sampling times are indicated from the **start** of infusion, while the timing of safety measures is indicated from the **end** of infusion.

14.1 Physical examination

Full physical examinations will be performed at the screening and final visit / ETV. Body weight (BW) will be also recorded. The following apparatuses/systems will be checked:

- General appearance
- Chest/respiratory
- Gastrointestinal
- Head, eyes, ears, nose and throat
- Heart/cardiovascular
- Lymph nodes
- Metabolic/endocrine
- Musculoskeletal/extremities
- Neck (including thyroid)
- Neurological/psychiatric
- Skin/dermatologic

Any abnormalities will be recorded.

Short physical examinations will be performed upon confinements (with measurement of BW), discharges and/or end of periods (without measurement of BW) ([Table 13.1.2](#)). Information about the physical examination will be recorded by the Investigator. The following apparatuses/systems will be checked:

- General appearance
- Chest/respiratory
- Heart/cardiovascular
- Lymph nodes
- Neurologic/psychiatric
- Skin/dermatologic

Any abnormalities will be recorded.

Significant findings/illnesses, reported after the start of the study and that meet the definition of an AE (see [§ 18](#)), will be recorded in the subject source documents.

Date of the physical examination, overall Investigator's interpretation (as normal or abnormal and, if abnormal, clinically significant or not clinically significant) and clinically significant abnormalities (if any) will be reported in the individual CRFs.

Subjects will be weighed (kg) lightly clothed without shoes. Height will be measured at screening only and BMI will be recorded. BMI will be calculated as weight [kg]/(height [m] x height [m]).

Physical examinations will be performed at the following times during the 2 study parts:

Part A

- Screening visit (Full physical examination)
- Upon confinement on Day -1 only if screening performed more than 7 days before (Short physical examination). BW will be measured on both occasions
- Upon discharge on Day 2 (Short physical examination)
- Final visit/ETV (Full physical examination)

Part B

- Screening visit (Full Physical Examination)
- Upon confinement on Day -1 of period 2 (Short physical examination). Also in period 1, only if screening performed more than 7 days before (Short physical examination). BW will be measured in both periods
- At the end of period 1 (Day 13) (Short physical examination)
- Final visit/ETV (Full physical examination)

14.2 Vital signs

Subjects' blood pressure (BP) and pulse rate will be measured by the Investigator or his/her deputy after 5 min at rest in sitting position.

Measurements will be performed at the following times during the 2 study parts:

Part A

- Screening visit
- Upon confinement on Day -1
- On Day 1, at pre-dose, at the end of the injection and 1, 2 and 4 h after the end of the injection
- Upon discharge on Day 2 (24 h after the end of the injection)
- Final visit/ETV

Part B

- Screening visit
- On Day 1 of each period and on Day 3 of period 1, at pre-dose, at the end of the injection/infusion and 1, 2, 4 and 24 h after the end of the injection/infusion
- Upon discharge on Day 5 of period 1 and on Day 3 of period 2 (48 h after the end of the injection/infusion)
- On Days 6, 7, 8, 9, 10, 11, 12, 13 of period 1 and on Days 6, 7, 8, 9, 10, 11 of period 2 (Ambulatory visits) (in period 2, coinciding with the final visit measurement)
- ETV

Actual measurement times for each subject will be recorded in the individual case report forms (CRFs). The actual times should not exceed the recommended tolerance ranges presented in the following table. Any deviation outside the recommended ranges will be verified through Data Clarification Forms and, if confirmed, will be reported as protocol deviation.

Table 14.2.1 Tolerance ranges for the measurements of vital signs

Scheduled time	Tolerance range
Pre-dose (0) of Day 1	2 h before the start of the injection/infusion
At the end of injection/infusion	+10 min
1, 2 h	+10 min
4 h	±1 h
24, 48 h	± 2 h

14.3 12-lead ECGs

14.3.1 12-lead ECGs recorded at the Phase I Unit for immediate safety evaluation

Triplicate 12-lead ECGs will be recorded in supine position after 5 min at rest by the Investigator or his/her deputy for immediate safety evaluations.

Triplicate 12-lead ECGs will be recorded at the following times during the 2 study parts:

Part A

- Screening visit
- On Day 1, at pre-dose, at the end of the injection and 1, 2 and 4 h after the end of the injection
- Upon discharge on Day 2 (24 h after the end of the injection)
- On Day 7, the final visit
- ETV

Part B

- Screening visit
- On Day 1 period 1, at pre-dose and 1 and 2 h after the end of the infusion
- On Day 2 of period 1 (24 h after the end of the infusion)
- On Day 3 of period 1 and on Day 1 of period 2, at pre-dose and 1 and 2 and 24 h after the end of the injection/infusion
- On Day 13 of period 1 and Day 11 of period 2 (in period 2, coinciding with the final visit measurement)
- ETV

Triplicate 12-lead ECG parameters and abnormalities will be recorded in the individual CRFs.

14.3.2 *Continuous 12-lead ECG*

In Part B, on each dosing day, a continuous 12-lead ECG will be recorded and discrete triplicate recordings will be extracted from the continuous Holter ECG monitoring for the data analysis.

Continuous 12-lead ECG will be recorded:

- On Day 1 period 1, from 1 h before to 48 h after the end of the infusion. In addition, discrete triplicate 12-lead ECGs will be extracted 3 times within 1 h before the start of infusion and at the end of the infusion and 0.5, 1, 2, 4 and 24 h after the end of the infusion
- On Day 3 of period 1 and on Day 1 of period 2, from shortly before the injection/infusion start to 48 h after the end of the infusion/infusion. In addition, discrete triplicate 12-lead ECGs will be extracted at pre-dose 3 times within 1 h before the start of the injection/infusion and at the end of the injection/infusion and 0.5, 1, 2, 4, 24 and 48 h after the end of the injection/infusion

ECG continuous recording will be performed using appropriate continuous 12-lead recording devices with the capacity for digital signal processing, adequately serviced and calibrated. For the ECG monitoring, the operator will always apply the same technique for skin preparation, lead placement and time of recording. Subjects will rest quietly in a fully supine position for at least 10 min before each scheduled timepoint for ECG evaluation. The provider (§ 7.5) will be in charge to provide the devices for continuous monitoring, to train the Phase I Unit personnel in the use of the device, to extract and to analyze the data. Triplicate 10-sec ECGs will be extracted within a time window of 10 min preceding coinciding PK sampling.

ECG tracings will be electronically stored and sent to the central ECG laboratory for analysis at the end of each period.

14.3.3 *Tolerance ranges for ECG recording*

Actual ECG recording times will be recorded in the individual CRFs. The actual times of recordings should not exceed the recommended tolerance ranges presented in the following table. Any deviation outside the recommended ranges, only in study Part A, will be verified through Data Clarification Forms and, if confirmed, will be reported as protocol deviation.

Actual times of the ECG recordings in Part B will be recorded, but no deviation from the scheduled times will be reported.

Table 14.3.1 Tolerance ranges for the discrete ECG recording in Part A

Scheduled time	Tolerance range
Pre-dose (0) of Day 1	1 h before the start of the injection/infusion
At the end of injection/infusion	+10 min
1, 2 h	+10 min
4 h	+1 h
24 h	+2 h

Date/time of the ECG recording, overall Investigator's interpretation (as normal or abnormal and, if abnormal, clinically significant or not clinically significant) and clinically significant abnormalities (if any) will be reported in the individual CRFs. All clinically significant abnormalities after the screening visit will be recorded as AEs. Hard copies of the ECGs will be attached to the CRF (See also § 16.3.1).

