Salivary alcohol test		X				X			
Vital signs	X		X ⁴	X ⁵	X	X	X ⁵	X	X
TriPLICATE 12-lead ECGs for immediate safety	X		X ⁶	X ⁷	X ¹⁰		X ⁷		X
Continuous ECG monitoring			X ⁸	X ⁹			X ⁹		
Eligibility evaluation		X							
Confinement		X	X	X		X	X		
Randomization		X							
Placebo administration			X ¹⁶						
Active treatment administration				X ¹⁷			X ¹⁶		
PK blood sampling¹¹				X	X		X	X	X
Discharge¹²				X			X		X
AEs monitoring¹³	X	X	X	X	X	X	X	X	X

1. At visit 2, only if screening physical examination performed more than 7 days before Day -1
2. Women only - serum b-HCG test
3. Women only - urine test
4. At pre-dose, end of the injection/infusion, then at 1, 2, 4 and 24 h after the end of the injection/infusion; to be measured after 5 min at rest (sitting position).
5. At pre-dose, end of the injection/infusion, then at 1, 2, 4, 24 and 48 h after the end of the injection/infusion; to be measured after 5 min at rest (sitting position).
6. At pre-dose and at 1, 2 and 24 h after the end of P injection/infusion; to be measured after subjects remained for 5 min at rest in supine position before recording.
7. At pre-dose and at 1, 2 and 24 h after the end of T/R injection/infusion; to be measured after subjects remained for 5 min at rest in supine position before recording.
8. Starting 1 h before P administration and up to 48 h after the end of the injection/infusion; discrete triplicate 12-lead ECGs to be extracted 3 times within 1 h before the start of injection/infusion and at the end of the injection/infusion and 0.5, 1, 2, 4 and 24 h after the end of the injection/infusion after 10 min at rest in supine position
9. Starting shortly before T/R administration and up to 48 h after the end of the injection/infusion; discrete triplicate 12-lead ECGs to be extracted 3 times within 1 h before the start of injection/infusion and at the end of the injection/infusion and 0.5, 1, 2, 4, 24 and 48 h after the end of the injection/infusion after 10 min at rest in supine position
10. On Day 13 only
11. See schedule in [Table 4.4](#)
12. In the morning after the 48-h post-dose blood sample collection, ECG recording and vital signs check
13. Starting at the screening visit, immediately after informed consent, up to the final visit/ETV
14. After the 240-h post-dose blood sampling on Day 11 of Period 2.
15. Upon discontinuation, in case of early termination
16. On Day 1
17. On Day 3

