Each subject will then receive T followed by R or R followed by T in period 1 and 2 respectively, according to the randomization schedule. The duration of T injection will be the one selected in study Part A, while R (diluted to 50 mL) will be administered in 30 min. A wash-out period of at least 28 days will elapse between the two consecutive administrations of T and R (28-day wash-out between Day 3 of period 1 and Day 1 of period 2).

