17.5.4 Vital signs

Vital signs values will be listed and summarized by descriptive statistics.

17.5.5 *Body weight*

Body weight values at screening and final visit/ETV will be listed and summarized by descriptive statistics.

17.5.6 *ECG for immediate safety*

Date/time of ECG recordings, overall investigator's interpretation (as normal or abnormal and, if abnormal, clinically significant or not clinically significant) and clinically significant abnormalities (if any) will be listed. The overall investigator's interpretation will be summarized using tables of frequency.

17.5.7 *Continuous ECG*

For the cardiac safety evaluation and further analyses, 10-sec triplicate ECGs will be extracted within a time window of 10 min preceding PK sampling and evaluated (§ 14.3).

The QT interval will be presented raw and after HR correction using the Fridericia formula as primary endpoint. ECG data will be listed and summarized highlighting differences from baseline for quantitative variables and frequencies of treatment emergent abnormalities. The number of QTc values above 450 ms, 480 ms and 500 ms at each evaluation timepoint will be tabulated, jointly with its change from baseline. Likewise, values differing by more than 30 ms from the baseline at each time point will be tabulated.

Data from Holter continuous recording will be assessed in blind by the provider (§ 7.5) according to a centralized procedure.

The primary analysis will be based on exposure response modeling of the relationship between netupitant and its metabolites M1, M2 and M3 and change-from-baseline QTcF (Δ QTcF) with the intent to exclude an effect >10 ms at clinically relevant plasma concentrations of netupitant, M1, M2 and M3.

In addition, the effect of netupitant on the placebo-corrected Δ QTcF, Δ HR, Δ PR, Δ QRS, Δ QT, and Δ QTcB ($\Delta\Delta$ QTcF, $\Delta\Delta$ HR, $\Delta\Delta$ PR, $\Delta\Delta$ QRS, $\Delta\Delta$ QT, and $\Delta\Delta$ QTcB) will be evaluated at each post-dose timepoint ('by timepoint' analysis) using the Intersection Union Test. An analysis of categorical outliers will be performed for changes in HR, PR, QRS, QT, QTcF, QTcB, T-wave morphology and U-wave presence.

See also § 16.3.1.

18 DEFINITION AND HANDLING OF AEs AND SAEs

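### Part B QT triplicates are tied to the 10 min before a PK sample, but ECG times run from the end of dosing and PK times from the start, so 4 of 7 post-dose ECGs after R fall 30 min from the nearest sample

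*Protocol*

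**What the plan says.** The protocol uses two clocks and says so. The note opening section 14 counts PK times from the start of infusion, "while the timing of safety measures is indicated from the end of infusion". Section 14.5.1 confirms the first: "All the scheduled samples will be collected at the given times counted from the start of the injection/infusion". Section 14.3.2 sets the Part B extractions after T and R "at the end of the injection/infusion and 0.5, 1, 2, 4, 24 and 48 h after the end of the injection/infusion", and Table 4.2 footnote 9 agrees. After placebo the list is the same but stops at 24 h (14.3.2; Table 4.2 footnote 8).

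The extraction rule then links the two: "Triplicate 10-sec ECGs will be extracted within a time window of 10 min preceding coinciding PK sampling" (14.3.2). Section 17.5.7 has "10-sec triplicate ECGs will be extracted within a time window of 10 min preceding PK sampling and evaluated", without the word "coinciding" but with a reference back to 14.3. Section 14.5.1 also expects ECGs to be cut before the blood sample of the same time point. Section 14.3.2 requires at least 10 min supine rest before each scheduled ECG time.

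For R, section 10.1.2 states "while R (diluted to 50 mL) will be administered in 30 min". The duration of T (2, 5, 15 or 30 min) comes from Part A, and P is given over the same duration as T. Tables 4.4 and 14.5.1.1 have no placebo column.

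**The concern.** The rule assumes that ECG and PK times fall together. With one clock at the end of dosing and the other at the start, they separate by the dosing duration unless a sample happens to lie at the shifted time. Nothing in the protocol reconciles them.

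The primary ECG analysis in 17.5.7 models change from baseline in QTcF on concentrations of netupitant, M1, M2 and M3, so it needs a concentration for each ECG. If the ECG keeps its scheduled time, several readings after R have no sample within the window. If it is moved to the PK sample, it is taken at a time other than its label and outside the supine rest that the protocol assures. Because 14.3.3 says that Part B departures from scheduled ECG times are recorded but not reported as deviations, the mismatch would not surface during conduct.

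**Working it through.** **Inputs.** Post-dose ECG times after T or R, in minutes from the end of dosing: 0, 30, 60, 120, 240, 1440, 2880 (14.3.2). PK times from the start, common to all Part B columns: 30, 45, 60, 90, 120, 180, 240, 480, 720, 1440, 2880 min and later. Shorter injections add earlier samples (15 and 20 min for a 15-min T; also 5 and 10 min for a 5-min T; also 2 min for a 2-min T).

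**Check of the PK count.** The 30-min column has 20 samples and the 2-min column 25. PK blood is 20×2×6 = 240 mL to 20×6 + 25×6 = 270 mL. Adding 4×12 = 48 mL of safety blood gives 318 mL. All three figures match section 14.6, and no volume is left for PK after placebo.

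**Conversion.** ECG time from start = dosing duration + ECG time from end.

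| Dosing duration | ECG times from start (min) | Minutes after nearest PK sample | Exact matches |
|---|---|---|---|
| 30 min (R, or T if selected) | 30, 60, 90, 150, 270, 1470, 2910 | 0, 0, 0, 30, 30, 30, 30 | 3 of 7 |
| 15 min (T) | 15, 45, 75, 135, 255, 1455, 2895 | 0, 0, 15, 15, 15, 15, 15 | 2 of 7 |
| 5 min (T) | 5, 35, 65, 125, 245, 1445, 2885 | 0, then 5 for each | 1 of 7 |
| 2 min (T) | 2, 32, 62, 122, 242, 1442, 2882 | 0, then 2 for each | 1 of 7 |

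After R, the samples following the four unmatched ECGs are at 3, 8, 48 and 72 h, so none of the four lies in the 10 min before any scheduled sample.

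**PK tolerances (Table 14.5.1.2).** These are ±2 min from 45 min to 2 h, ±5 min from 3 to 24 h and ±60 min from 48 h. After R, only the 48-h sample could be drawn at 48.5 h within tolerance, leaving 3 of 7 unmatched.

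**Supine rest, R reading labelled 2 h.** On the ECG clock the assured 10 min of rest are 140–150 min from start. The 10 min before the 2-h PK sample are 110–120 min. They do not overlap.

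**End-of-injection reading, short T.** The 10 min before the 2-min sample run from 2 − 10 = −8 to 2 min; before the 5-min sample, from 5 − 10 = −5 to 5 min. Part of each window is pre-dose.

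**What 30 min does to concentration.**
- Netupitant: mean levels stay nearly constant to 4 h (8.2.1.1). Later, with mean half-lives of 35–55 h, 1 − 2^(−0.5/35) = 1.0% and 1 − 2^(−0.5/55) = 0.6%.
- Metabolites at 24 and 48 h: with mean half-lives of 111.4–159.54 h, the same formula gives 0.3% to 0.2%.
- M1 and M3 before their median peak at 12 h: assuming a linear rise from zero, 4.5/4 − 1 = 12.5% from 4 to 4.5 h and 2.5/2 − 1 = 25% from 2 to 2.5 h. A rise that flattens towards the peak gives less.

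**The case against.** The strongest reply is that the rule applies only where a PK sample coincides. Section 14.3.2 says so, and 17.5.7 refers back to 14.3. Other extractions then keep their nominal times, actual ECG and PK times are both recorded, and pairing can be settled in the analysis plan. The ECG objectives concern T and the comparison with placebo, not R, and for a 2- or 5-min T the offset is 2 or 5 min.

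Much of this stands. It limits the size of the problem, and the R count matters less if the model uses T alone, although 17.5.7 states no such restriction. But this reading leaves the non-coinciding extractions with no stated window, and after R with no concentration within 30 min apart from the movable 48-h sample. An analysis plan can choose a pairing; it cannot supply supine rest or a sample that the protocol did not schedule.

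A reader might infer that placebo ECGs are defective because no PK is drawn. The documents do not support that: placebo needs no concentration, and its ECGs can be cut from the continuous recording at nominal times. Only the window is undefined, so it could differ from that for T. Nor do by-timepoint comparisons necessarily mix different true times. If extractions keep their scheduled times, P and T share duration and labels and therefore match on either clock.

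**Conclusion.** The point holds as a conflict of schedules that should be reconciled before conduct. After R, 4 of 7 post-dose ECGs (57%) fall 30 min after the nearest scheduled sample, or 3 of 7 if the 48-h sample is moved within tolerance. A 30-min T has the same mismatch, and a 15-min T has 5 of 7 readings 15 min off. For a 2- or 5-min T the later readings are nearly aligned, but the ECG paired with the end-of-injection concentration may be pre-dose.

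A reader might infer from these counts that more than half of the R data are biased or that the QT analysis is invalid. They do not show that, because they count timing mismatches. For netupitant the likely effect is small, about 1% or less at 24 and 48 h and little at 2 and 4 h. For M1 and M3 it is larger at the 2-h and 4-h readings, about 12% from 4 to 4.5 h if the rise is linear. The late figures assume that the mean terminal half-lives already apply at 24 h.

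**What to change.** In 14.3.2, 17.5.7, Table 4.2 footnotes 8 and 9 and the synopsis:

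- Put the Part B continuous-ECG extractions and their supine rest on the PK clock: end of dosing, then 0.5, 1, 1.5, 2, 4, 24 and 48 h from the start of dosing. Every Part B column of Table 4.4 has a sample at each of these times.
- Keep the 0.5-h reading for T and P. A list starting at 1 h would leave no ECG between the end of a short injection and 1 h. For a 30-min infusion, 0.5 h is the end of dosing.
- Use the same nominal times for placebo up to 24 h, with the window defined by nominal time.
- Give the end-of-dosing reading its own window that does not extend before dosing.
- Leave the on-site safety ECGs unchanged.

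The cost is protocol wording and matching text in any ECG analysis plan. No blood draw or new recording is needed. Rest periods after R move by up to 30 min, so they no longer all line up with the on-site safety ECGs. R keeps 7 post-dose readings; a short T goes from 7 to 8 and a short P from 6 to 7, one extra extraction each from the existing recording.
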